Propranolol has been used for different indications for many years. Most recently, propranolol gained FDA approval for use in infants with hemangiomas, a related vascular anomaly (Hemangeol ®) (<http://www.accessdata.fda.gov/scripts/cder/drugsatfda/index.cfm?fuseaction=Search.DrugDetails>, accessed May 23, 2014). FDA-approved dose range for treating hemangiomas in infants (>5 weeks old, >2kg) ranged from 1-3mg/kg/day in divided doses. Propranolol has also been used to treat pediatric supraventricular tachycardia at doses up to 4mg/kg/day[3, 4]. However,  $\beta$ AR antagonists are not without potential adverse effects, including hypotension, bradycardia, hypoglycemia, bronchospasms, and sleep disturbances[5].

The dose range of 0.7-1mg/kg/day was chosen for our LM patients as it was the low end of dose range for infants treated with propranolol for problematic hemangiomas. At this dose, no significant hemodynamic adverse effects were noted in our LM patients. However, when patients stopped propranolol or their dose fell below 0.7mg/kg/day, they suffered rebound worsening of their symptoms. Moreover, inflammatory events such as infections temporarily overcame the effects of 0.7-1mg/kg/day of propranolol. Thus, it is unknown whether we have achieved maximum propranolol efficacy at our current dose range. We propose to escalate propranolol dosages up to 3mg/kg/day in this study, still well below the dose ranges currently used in clinical settings.

In this clinical trial, we will examine whether QMR can quickly and accurately quantify lymphedema severity, as well as evaluating whether we have optimized propranolol usage for treatment of LM patients. The primary endpoints for this study are to: 1) validate QMR as a tool for evaluation of lymphedema, and 2) ascertain whether LM patients can tolerate higher doses of propranolol, as measured by known propranolol adverse effects and patient-reported symptoms. A secondary endpoint will address whether patient-reported LM symptoms and quality of life are improved with higher doses of propranolol; objective findings such as LM size on physical examination and imaging studies will be analyzed as well. In addition, LM tissue biopsies will be acquired from patients before and after propranolol treatment for further analyses of disease progression.

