## 6.0 DOSE MODIFICATIONS FOR ADVERSE EVENTS

**The Study Chair must be notified of any dosage modification.**

### 6.1 Dose Modifications for Potential Propranolol Specific Side Effects

#### 6.1.1 Hypotension and Bradycardia

**Baseline blood pressure (BP)** is defined as the blood pressure obtained at the examination used for study enrollment. This baseline BP should be obtained as follows: 1) Obtain 3 serial blood pressures from the same extremity with the patient in the same position that are separated by at least 5 minutes. Avoid using the lower extremity if possible. BP will not be obtained from the affected limb. 2) Average the systolic blood pressure from the 2nd and 3rd measurements. 3) Average the diastolic blood pressure from the 2nd and 3rd measurements. 4) The baseline BP is the average of the systolic over the average of the diastolic measurements.

Heart rate will be measured by palpation of the radial pulse serially from the same extremity for 15 secs, separated by at least 5 minutes. In the case of extremity LMs, pulse rate will not be obtained from the affected limb. 2) Average the pulse rate from 2nd and 3rd measurements.

6.1.1.1 Patient must have no evidence of clinical contraindications with normal HR and BP parameters prior to dose escalation occurring. If individuals are found to have a fall in their blood pressure or heart rate to below normal limits, but asymptomatic:

- a. patient will be not have dose escalation
- b. patient will be evaluated for dose escalation at the next 2-week cycle.
- c. if HR and BP fall below normal ranges and patient is symptomatic, propranolol will be held for 2 weeks, and re-introduced at the next visit at the lowest tolerated dose.
- d. if patient is at the lowest dose already (0.5mg/kg/day), they will be pulled from the study and re-evaluated at the next visit.
- e. Patients receiving 0.5mg/kg/day who experience HR or BP decrease below the normal range at 4 weeks must be taken off protocol therapy.

Table 5. Side effects and propranolol dosing guidelines

Hypotension and Bradycardia	Propanolol Dosing Guidelines
Within normative range	No change in dose
Below normal range, asymptomatic	Cardiology evaluation, EKG, echocardiogram; if cardiac status is acceptable, patient will not have dose escalation and remain at current dose level with subsequent re-evaluation at 2 weeks

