Below normal range, symptomatic	Discontinue propranolol (off protocol therapy. Re-evaluate after 2 weeks. If HR and BP then fall within normal parameters they will be reintroduced to the study with dose de-escalation to the prior tolerated dose of propranolol. If HR/BP below normative range at 0.5mg/kg/day, patient will be removed from study)

Hypoglycemia	Management/Next Dose for propranolol
Blood glucose >80 mg/dl	No change in dose
Blood glucose <80, >60, asymptomatic	Clinical evaluation, review feeding schedule, repeat test after more

Hypoglycemia	Management/Next Dose for propranolol
	frequent/supplemental feeds
Blood glucose <80, symptomatic	Discontinue propranolol (off protocol therapy)

Bronchospasm	Management/Next Dose for propranolol
Transient/self-limited episode	Clinical evaluation, may continue at same dose
Associated with URI	Hold propranolol till URI resolves; if >7 days, off protocol
Not associated with URI, persistent or requiring new medical treatment	Discontinue propranolol (off protocol therapy)

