**Table 6. Study schedule and evaluations**

STUDIES TO BE OBTAINED	Pre-Study	Wk 1	Wk 2	Wk 3	Wk 4	Wk 5	Wk 6	Wk 7	Wk 8
Informed consent	x								
Demographics	x								
Medical history	x								
Questionnaires	x	x	x		x		x		x
Physical exam	x	x	x		x		x		x
LM measurements	x	x	x		x		x		x
Vital signs	x	x	x		x		x		x
Height	x	x	x		x		x		x
Weight	x	x	x		x		x		x
CBC w/diff, platelets	x				x				x
Cr	x				x				x
Blood glucose	x	x a	x a		x a		x a		x a
EKG	x	x a	x a		x a		x a		x a
Echocardiogram a	x								
serum $\beta$ -HCG for females of childbearing potential	x								
Adverse event evaluation	x	x	x	x	x	x	x	x	x
Skin Biopsies	x								x
CXR a	x								
MRI	x								x
QMR	x								x
Body water content evaluation	x								x

aIf clinically indicated after initial evaluation

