## 8.4 Statistical Analysis

Descriptive statistics will be used to summarize patient characteristics, toxicity data, response data and biomarker expression. Toxicity rates at each dose tested will be presented with 95% exact confidence intervals. Responses will be evaluated among patients treated at the highest tolerable dose. Continuous outcomes will be summarized using mean  $\pm$  standard deviation or median (interquartile range) for non-normal data. Comparisons between groups and response changes from baseline will be evaluated using two-sided t-tests or the non-parametric equivalent Wilcoxon Rank-Sum test (for non-normal data). Association between PIK3CA mutational status and patient response will be assessed using chi-square/Fisher exact test. All analyses will be performed using a type I error of 0.05. Biostatistics will be done using Irving Institute for Clinical and Translational Research statistical services at Columbia University Medical Center.

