## **10.0 CRITERIA FOR REMOVAL FROM PROTOCOL THERAPY AND OFF STUDY CRITERIA**

10.1 **Criteria for Removal from Protocol Therapy**

- Intercurrent illness that prevents further administration of treatment.
- Adverse Events requiring removal from study (See Section 6.0).
- Refusal of further protocol therapy by patient/parent/guardian

- d) Non-compliance that in the opinion of the investigator does not allow for ongoing participation.
- e) Completion of 2 months of therapy.
- f) Physician determines it is not in the patient's best interest.

Patients who are off protocol therapy are to be followed until they meet the criteria for Off Study (see below). Ongoing adverse events, or adverse events that emerge after the patient is removed from protocol therapy, but within 30 days of the last dose of investigational agent, must be followed until resolution or stabilization of the adverse event. Follow-up data will be required unless consent is withdrawn.

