#### 11.5 **Reporting and Exclusions**

All of the patients who met the eligibility criteria (except those who received no propranolol) will be included in the main analysis of the response. All conclusions will be based on all eligible patients.

Sub-analyses may then be performed on the basis of a subset of patients, excluding those for whom major protocol deviations have been identified. However, these sub-analyses will not serve as the basis for drawing conclusions concerning treatment efficacy, and the reasons for excluding patients from the analysis will be clearly reported.

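### Section 8.4 limits the response analysis to patients at an undefined highest tolerable dose, while Section 11.5 makes all eligible treated patients the main response population

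*Combined protocol and SAP*

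**What the plan says.** Two sections state who enters the response analysis.

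- Section 8.4 (Statistical Analysis): "Responses will be evaluated among patients treated at the highest tolerable dose". The sentence has no qualifier, and no section defines the dose it refers to.
- Section 11.5 (Reporting and Exclusions) states that all eligible patients ("except those who received no propranolol) will be included in the main analysis of the response". It adds: "All conclusions will be based on all eligible patients".

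Neither section refers to the other. Section 12.4.1 sets evaluability by type of measure: subjective response needs questionnaires at baseline and at the last visit, and objective response needs the examination and imaging. It does not say which population is the main one.

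The dosing rules decide who is on which dose at the end. Section 5.1 makes Week 6 the last planned increase, to 3 mg/kg/day. Patients who twice fail a later step stay at the highest dose they tolerated (14.2.3). For low heart rate or blood pressure with symptoms, 6.1.1.1(c) says "propranolol will be held for 2 weeks, and re-introduced at the next visit at the lowest tolerated dose", and Table 5 discontinues the drug with the instruction "Re-evaluate after 2 weeks". Table 5 also stops propranolol for symptomatic hypoglycemia and for persistent bronchospasm not linked to a respiratory infection. Table 6 places the second MRI, QMR and "Body water content evaluation" at Week 8.

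**The concern.** Under 11.5, membership depends on eligibility and on having taken any drug. Under 8.4, it depends on how well the patient tolerated the drug, which is known only after baseline. An analyst working from the statistical analysis section alone would report response in a group selected on tolerance. An analyst working from 11.5 would not. The PIK3CA comparison in 8.4 also uses patient response, so its denominator would move too.

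The choice is probably not neutral. The Abstract reports that "when patients stopped propranolol or their dose fell below 0.7mg/kg/day, they suffered rebound worsening of their symptoms". Section 2.1 describes one lymphedema patient whose swelling returned to its pre-treatment level after stopping, and another whose symptoms came back when the dose was halved. If patients who are off drug or on a reduced dose at Week 8 look worse for that reason, leaving them out makes the reported response more favourable. Settling the population after the data are seen would leave that choice open.

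**Working it through.** The plan attaches no figure to this point, so there is none to reproduce. The check sets the two rules side by side and follows the dosing rules to Week 8.

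**Step 1. What could 8.4 mean?** Three readings are possible.

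- A: one study-wide dose, for example 3 mg/kg/day. The preceding sentence of 8.4 speaks of toxicity at each dose, which leaves this open. No section gives a rule for choosing such a dose.
- B: each patient's own highest tolerated dose, as taken at Week 8. The patient-level wording of 14.2.3 supports the own-dose part. The Week 8 part is an inference from the timing of the assessments.
- C: having been treated at one's own highest tolerated dose at some time.

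**Step 2. Who is in each set?**

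| State at Week 8 | 11.5 | 8.4, A (3 mg/kg/day) | 8.4, B | 8.4, C |
|---|---|---|---|---|
| Taking 3 mg/kg/day | in | in | in | in |
| Held at a lower dose and taking it | in | out | in | in |
| Restarted below own highest tolerated dose | in | out | out | in |
| In a 2-week hold that began at Week 6 | in | out, unless a single 3 mg/kg/day dose counts | out | in |
| Stopped for hypoglycemia or bronchospasm | in | out, unless 3 mg/kg/day was reached first | out | in |
| Never tolerated 0.5 mg/kg/day | in | out | out | doubtful |

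Only reading C brings the two sets close together.

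**Step 3. Do the rules produce the off-drug state?** Yes. Week 6 + 2 weeks = Week 8. A patient held at Week 6 under 6.1.1.1(c) comes to the Week 8 assessments after 2 weeks without drug.

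**Step 4. Do they produce the restarted-lower state?** Under 6.1.1.1(c), yes. Suppose a patient tolerates 0.5 and 1 mg/kg/day and has symptomatic low values on the first 2 mg/kg/day dose at Week 4. The hold ends at Week 4 + 2 = Week 6. Read literally, (c) restarts at 0.5, the lowest tolerated dose. Table 5 restarts at the prior tolerated dose, here 1. At Week 8 the patient in the first case is on drug but below the personal highest tolerated dose. That patient is also below the 0.7 mg/kg/day under which the Abstract reports rebound.

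**Step 5. Would these patients have Week 8 data?** Section 10.1 keeps patients who are off therapy in follow-up and requires follow-up data unless consent is withdrawn. No sentence says explicitly that they have the Table 6 Week 8 assessments. Patients removed from the study, such as those who fail 0.5 mg/kg/day twice, may have none, yet 11.5 still counts them.

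**Step 6. How many?** The documents give no rate of symptomatic holds or Table 5 stops, so the number cannot be derived. Planned enrolment (11.1) is 15-20, so one patient is between 1/20 = 5% and 1/15 = 6.7% of the cohort. That is a patient's weight in the denominator and not an estimate of any effect.

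**The case against.** The best defence is that the plan largely answers the question. Section 11.5 is the only place that names a main response analysis, and 8.4 never calls its own set main or primary. This stands in part: a reader might infer that the plan gives no indication of which set counts, and that goes too far. But 8.4 states its population without qualification, in the statistical analysis section, and does not present it as supportive.

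Second, 8.4 contains no condition of being on drug at Week 8. A reader might infer that it certainly excludes off-drug patients. The text does not support that certainty, because reading C keeps them. What stands is that the term is undefined and two of its three readings conflict with 11.5.

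Third, the off-drug path is narrow. Patients with low values but no symptoms stay on drug (6.1.1.1, Table 5). Section 5.2.2 sends a patient whose values fall 2 hours after a new dose home on the current dose. Only symptomatic low values around Week 6, or a Table 5 stop, leave a patient off drug at the Week 8 visit. If stopped patients have no Week 8 scan, their imaging problem is missing data under either section. Both points are correct and limit the number affected. They do not reconcile the two rules.

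Fourth, 10.1 already requires follow-up data. It does, but without naming the Week 8 assessments.

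**Conclusion.** The two sections state conflicting response populations unless 8.4 is given an ever-treated meaning that it does not express. Following 8.4 under either other reading would select patients on tolerance after baseline and contradict 11.5.

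The likely direction is a more favourable response under 8.4. This assumes that the rebound reported in the Abstract and in Section 2.1 would show in the Week 8 measures. Those accounts rest on the sponsor's own early experience, and the return to pre-treatment level on one patient, with no time course given. Rebound within a 2-week hold is therefore plausible but not documented.

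The size cannot be computed. A reader might try to build it from figures in the protocol, but none of them fits:

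- The reduction of more than 20% in 11.2.1 describes children who responded and is not a mean over all patients on drug.
- The 70% in the Abstract is reported symptom improvement, and the plan sets no responder cut-off.
- The Table 7 rates for hypotension (2.8%) and bradycardia (0.9%) are overall frequencies of asymptomatic events in infantile hemangioma. They are not rates per dose step, and events without symptoms would not trigger the hold.

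Nor do the documents show that any reported response will be biased.

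Severity is minor: response is a secondary endpoint, no stated sample size or power depends on it, and 11.5 already points to the right population.

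**What to change.** Make two changes by amendment, before the data are analysed.

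1. Replace the 8.4 sentence with: *The main response analysis uses the population in 11.5; an analysis limited to patients taking propranolol at their own highest tolerated dose at Week 8 is supportive only.* This removes the conflict, defines the dose at patient level in line with 14.2.3, and keeps the on-dose question as a labelled secondary look.
2. Add to 8.1: *Patients who stop early, and who remain in follow-up under 10.1, are asked to attend the Table 6 Week 8 assessments unless consent is withdrawn.* Without this, 11.5 counts patients for whom no response may have been measured.

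No test is added to Table 6. The cost is a few return visits for MRI, QMR and the fasting deuterium and bromide test, which some stopped patients will decline. The reported response may also be smaller, because patients measured after stopping or on a reduced dose stay in the main result.

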# 11.0 STATISTICAL AND ETHICAL CONSIDERATIONS

## 11.1 Sample Size and Study Duration

**Sample Size:** Based on our current clinical volume, we anticipate a total enrollment of 15-20 (this is just an example to show a range) patients over a period of 24 months.

**Accrual Rate:** We anticipate that 8-10 patients per year will be accrued to the study.

**Accrual Targets:** LMs affect the general population without known differences in genders or ethnicities. Therefore, we expect accrual to reflect the makeup of the population in the region(s) surrounding our institution.

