## 11.2 Study Design/ Endpoints (Table 2)

11.2.1 **Study design:** Each patient will serve as his/her own control, for comparison of study questionnaires (subjective) and with changes in the clinical measurements and imaging measurements of the anatomic area affected by lymphatic malformation compared before and after treatment (objective). In our experience, children exhibiting responses to propranolol displayed these within 2 weeks of beginning propranolol treatment, with estimated reduction in the overall volume of the affected area exceeding 20%.

11.2.2 **Primary endpoints:** The primary endpoint will be the tolerability of escalating dosage of propranolol both by subjective reporting (survey instrument) as well as objective measurements of vital signs. Survey instruments include a general quality of life (QOL) and function survey (SF-36), as well as validated survey instruments for patients with lymphedema (LYMPH—ICF, LYMPH—LCF—LL)[38, 39].

11.2.3 **Secondary endpoints:** The secondary endpoints of the study will be both subjective and objective evaluation of the lymphedema after propranolol treatment, as measured by both survey instrument and objective measurements (clinical exam and radiological studies), as well as biological assays from tissues obtained from biopsies.

11.2.3.1 We will determine whether higher doses of propranolol are well tolerated in this patient population. Secondarily, we will measure determine whether higher doses correlate with improvement in lymphedema symptoms and signs, and healing or improvement of skin lesions, if present (reduced lymphatic leakage, reduced bleeding). Skin lesions will be photographed at clinical visits, and daily lymphatic fluid losses estimated by weight measurements.

Using MRI and body composition analysis, we will determine whether propranolol decreases lymphedema, alters edema water content and location (intracellular vs. interstitial), or alters adiposity of affected extremity.

We will study the biologic activity of oral propranolol against lymphedema, by examining the expression of progenitor cell markers, lymphatic endothelial cell markers, beta-adrenergic receptor expression, macrophage markers and detection of adipocyte content of biopsy specimens (see table below). Results will be compared to ultrasound and magnetic imaging data.

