**Table 3. Markers to be probed and assessed in blood and tissues**

Progenitor cell markers	CD133, CD45, podoplanin, CD90, NG2
Lymphatic endothelial cell markers	VEGFR-2, VEGFR-3, podoplanin, Prox1, LYVE1
Beta-adrenergic receptors	Beta-1, beta-2, beta-3 adrenergic receptors
Macrophage markers	CD68, iNOS, F4/80

The analyses we plan to perform on the specimens have been validated by our laboratory using discarded de-identified specimens[14]. Fixed frozen tissue will be prepared and 5-micron sections generated. Standard immunohistochemistry will be performed with commercially available antibodies and H&E staining performed. Results will be captured by microscopy and digital camera. Results will be quantified using ImageJ software and *Student's t-test* to determine significance, with a  $p < 0.05$  considered significant. We have already isolated similar specimens from  $> 10$  patients and have obtained consistent results using these methodologies.

We have comprehensive data on *in vitro* and *in vivo* analysis of 12 cell lines from patients with LMs. We have demonstrated consistently that LMPCs have unique characteristics by FACS analysis and gene expression profile analysis. They express mesenchymal stem cell markers CD90 and NG2, and can be differentiated into various terminal cell types including adipocytes, mural and endothelial cells. When implanted into immunocompromised mice, these LMPCs formed cystic structures that phenocopy lymphatic malformations. These features are reproducible between LMPC cell lines, and demonstrate consistent changes in gene and protein expression after treatment with propranolol.

We are expecting to recruit 20 patients into this study. Our assays are sufficiently sensitive to detect 5-10% differences in proliferation rate and gene and protein expression changes.

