#### 11.3.3 Patient-Reported Outcomes; Symptom Assessment etc.

Patients' self-reported tolerance to propranolol will be assessed using validated quality of life (QOL) health surveys (SF-36, Lymph-ICF, Lymph-ICF-LL) SF-36 is an accepted general health status survey[38, 39]. Lymph-ICF and Lymph-ICF-LL are validated, disease-specific survey instruments for patients with lymphedema that evaluate physical and mental activity, impairments in function and activity limitations related to lymphedema.

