#### 12.4 **Response**

Patients should be re-evaluated for response by clinical examination every 2 weeks. Baseline MRI will be obtained, and an MRI repeated at 8 weeks. Response will be evaluated in this study using quality of life survey instruments, physical examination and radiologic studies (MRI at baseline and 8 weeks).

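### Beyond descriptive summaries, the survey half of the primary tolerability endpoint gets only a difference test, which in 15-20 patients cannot show that higher doses are tolerated

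*Combined protocol and SAP*

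**What the plan says.** Section 11.2.2 defines the endpoint: "The primary endpoint will be the tolerability of escalating dosage of propranolol both by subjective reporting (survey instrument", with vital signs as the objective half. The instruments are SF-36, Lymph-ICF and Lymph-ICF-LL. Section 11.3.3, which sits under the secondary endpoints, repeats that "self-reported tolerance to propranolol will be assessed using validated quality of life (QOL) health surveys". It gives no score change, cut-off, margin or per-patient rule.

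Section 12.4 puts the same instruments to a second use: "Response will be evaluated in this study using quality of life survey instruments, physical examination and radiologic studies". Section 8.4 then supplies the methods. Continuous outcomes get a mean and SD, or a median and interquartile range. Inference is "Comparisons between groups and response changes from baseline will be evaluated using two-sided t-tests", "or the non-parametric equivalent Wilcoxon Rank-Sum test (for non-normal data". On the error rate: "All analyses will be performed using a type I error of 0.05". Exact 95% intervals are planned at each dose, but for toxicity rates only, and no section turns a survey score into a toxicity.

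On size, 11.1 says "we anticipate a total enrollment of 15-20 (this is just an example to show a range) patients over a period of 24 months", and 11.3.1 says "We are expecting to recruit 20 patients into this study". Section 11.2.3.1 commits the trial to deciding if patients tolerate the higher doses.

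**The concern.** A difference test can show that scores got worse. It cannot show that they did not, because failure to reject is the expected result of a small sample. Here failure to reject would be the favourable answer, and the plan offers nothing else on the survey side that could support a statement of tolerance.

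An average also mixes two effects. Aim 1.2.1a uses Lymph-ICF and Lymph-ICF-LL to measure benefit, so improvement in some patients can offset intolerance in others.

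The analysis set adds to this. Section 12.4.1 keeps only patients with a baseline and a last-visit questionnaire, and 8.4 assesses response among patients at their highest tolerable dose. A patient who stops because of poor tolerance and misses the last questionnaire drops out of the survey analysis, which would make the average look better.

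**Working it through.** **Inputs from the plan.** Two-sided test at 0.05 (8.4); within-patient comparison (11.2.1); n = 15 to 20 (11.1).

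**Assumptions, because the plan gives no values.** Noise SD of the change score = 1; no dropout; one in five patients (3 of 15, 4 of 20) worsens by a fixed amount.

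**1. The plan's own figure.** There is no power, detectable change or statistical derivation of n to reproduce. The only check is accrual: 8-10 per year × 2 years = 16-20, in line with 15-20.

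**2. A uniform drop in the mean.** Paired t-test, noncentrality = d√n.
- n = 15, d = 0.5: 0.5 × √15 = 1.94, critical value 2.145, power 0.438, so non-significant in 56% of trials.
- n = 20, d = 0.5: 0.5 × √20 = 2.24, critical value 2.093, power 0.565, so non-significant in 44%.
- 80% power needs a mean drop of 0.78 SD (n = 15) or 0.66 SD (n = 20).

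**3. One in five worsens, the others unchanged on average.** The mean moves by only 0.2 × 1.5 = 0.3 or 0.2 × 2 = 0.4. Share of trials that are non-significant (simulation, 200,000 runs):

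| n | drop of 1.5 SD | drop of 2 SD |
|---|---|---|
| 15 | 88.6% | 86.0% |
| 20 | 84.5% | 79.6% |

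If the other patients improve by 0.25 SD, a 2 SD drop in one in five goes undetected in about 97% of trials at either n.

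The noise-free limit shows why. If a fraction p worsens equally and the rest do not change, t = √(n−1) × √(p/(1−p)). For 3 of 15, √14 × 0.5 = 1.87, below 2.145 however large the worsening. For 4 of 20, √19 × 0.5 = 2.18, just above 2.093.

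The non-parametric option does not help. For a 2 SD drop, the rank-sum test detects worsening in 4% (n = 15) or 6% (n = 20) of trials, assuming a correlation of 0.5 between baseline and week 8. The signed-rank test detects it in 12% or 17%.

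**4. What a confidence interval would say.** The half-width is t/√n times the observed SD: 2.145/√15 = 0.55 SD and 2.093/√20 = 0.47 SD. When one in five drops 2 SD, the 95% CI for the mean change fails to exclude a worsening of 0.5 in about 98% of trials at either n. The 0.5 is only a yardstick; the plan has no margin. By symmetry with step 2, with no drug effect at all the interval still fails to exclude it in 56% (n = 15) or 44% (n = 20).

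**5. What a per-patient count would say.** 3/15 = 20% (exact 95% CI 4.3-48.1%); 4/20 = 20% (5.7-43.7%). Noise also moves patients past a threshold. With a threshold of 1 SD, each unaffected patient passes it with probability 0.159, so with no drug effect 4 or more of 20 count as worse in 39% of trials. When four of 20 truly drop 1.5-2 SD, the lower limit exceeds that 16% background in only about 10-16% of trials.

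**The case against.** The strongest reply is that the t-test was never meant for tolerability. Section 8.4 separates toxicity from response data, applies the test to response, and looks at response only at the highest tolerable dose, when tolerance is already settled. Tolerance is judged patient by patient: 5.2.2 asks about dizziness and increased fatigue before escalation, adverse events are assessed weekly (Table 6), every treated patient is evaluable for them (12.1), and toxicity rates carry exact intervals.

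Much of this stands, and it rules out four stronger readings that a reader might infer.
- That the plan treats p>0.05 as tolerated: no section says so. The reading is left open, not prescribed.
- That a test of the mean is the only analysis: 8.4 also plans descriptive summaries and a rank test, although neither counts the patients who worsened.
- That patients who cannot tolerate a dose would go unseen: adverse-event grading is a separate route and may catch some of them.
- That a per-patient count would plainly expose the problem: step 5 shows that, under the same noise, it is no clear improvement as a test.

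The reply does not fill the gap. The adverse-event route and the escalation rules do not use the survey scores, yet 11.2.2 makes those scores half of the primary endpoint. If the test is for efficacy only, the survey half has no inferential analysis at all.

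**Conclusion.** The concern holds in this limited form: the survey half of primary tolerability has no criterion, and the one inferential method that reaches it cannot support a statement that higher doses are tolerated. At the planned size, non-significance is roughly an even chance for a true mean drop of 0.5 SD, and is the usual result (about 80-89% of trials) when one in five worsens by 1.5-2 SD. These figures rest on an assumed noise SD of 1, no dropout, exactly one in five affected and the others unchanged; improvement in the others raises them. The plan should be changed on this point. It is more than missing detail, because interval estimates from the same data would lead to a different statement (step 4).

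**What to change.** In 8.4, for the survey component of tolerability:
- Report, at each dose visit, the mean change from the pre-treatment score with its 95% CI, using all treated patients with a questionnaire at that visit.
- State that p>0.05 is not evidence of tolerance.
- Add, as a descriptive supplement, the number and proportion of patients worse by more than an amount that the sponsor fixes per instrument in advance, with the exact 95% CI. Say that without a control arm some patients will pass any threshold through measurement noise, so the count is not a test.
- Keep the t-test for efficacy, with the signed-rank test as its non-normal alternative. The rank-sum test compares two independent groups, whereas here each patient is their own control.

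No new data are needed, because Table 6 already schedules questionnaires before treatment and at weeks 1, 2, 4, 6 and 8. The cost is one extra table and a threshold to choose for each instrument. The tolerability statement will also be less favourable: at this size the interval will often fail to exclude a moderate worsening even if the drug has no effect on the scores.
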